Shrinking the Size of the Tobacco Power Wall and Restricting the Number of Tobacco Products Displayed to Reduce Adolescent Tobacco Use

NCT04632030

August 17, 2023

Study Protocol

Study objective. The overall objective of this research is to experimentally evaluate legally viable approaches to reducing the impact of the POS retail environment on adolescent risk of using four classes of tobacco products: cigarettes, ENDS, smokeless tobacco, and LCCs. Specifically, we propose to investigate the extent to which reducing the size of the tobacco powerwall display reduces adolescents' risk of future use of tobacco.

Study design. The experimental conditions that we will compare in this study are: large power wall with a large number of products (status quo/control), small power wall with a small number of products displayed, and a medium sized power wall with a medium number of products displayed. The studies will take place in the RAND StoreLab (RSL), a life-sized replica of a convenience store that was developed to experimentally evaluate how altering aspects of tobacco advertising at POS influences tobacco use.

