Methods. The study was approved by the RAND Human Subjects Protection Committee. Young people were recruited from the community through standard advertising campaigns. Interested individuals completed a telephone screening to determine eligibility. Eligible individuals completed informed consent (or consent and assent if minors). Participants completed a baseline questionnaire that assessed demographics, tobacco product cognitions, smoking and tobacco use, and convenience store shopping habits. Participants were then randomized to one of the three experimental conditions. They were provided with a \$10 (fake) RSL gift card and asked to shop in the RSL for whatever they wanted, for as long as they wanted. They were asked to purchase at least one item and check-out and pay for the item(s) as they would in any convenience store. A confederate who was not involved in the consent or survey process served as the cashier. This cashier scanned the selected items for a total price, scanned the gift card, and bagged the items. Although no participants attempted to purchase tobacco from the RSL in this study, any such attempts would have been met by the cashier with a request for age identification and the purchase attempt would have been declined (i.e., because no participants were ≥ 21 years old). After exiting the RSL, participants completed the dependent measures. They then: underwent a graduated debriefing; were asked to guess the study's purpose; and were told that they would be unable to retain the items they selected from the RSL. Participants then viewed a short tobacco media literacy video and received printed smoking prevention materials. Finally, they received a \$40 gift card as compensation.

Statistical analysis plan

First, we evaluated whether randomization distributed pre-shopping baseline characteristics evenly across the experimental conditions. These univariable analyses used either t-tests or chi-squared tests to evaluate significance (depending on variable distribution). Next, we used logistic regression to evaluate the relationship between the experimental conditions and post-RSL shopping risk of using cigarettes; ENDS LCCs, and smokeless tobacco. Lifetime use of each product under investigation was included in the appropriate model as a covariate (0 = no use; 1 = any lifetime use). Finally, because both age (continuous) and education (0 = still in middle/high school; 1 = high

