school graduate or more) are related to tobacco use, these variables were also included as covariates. Each reduced tobacco powerwall condition was compared to the all status quo/control condition (reference) using planned contrasts.

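### Each product's logistic model leaves out recorded use of the other tobacco products, which pulls the conditional odds ratio towards 1 and costs some power

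*Combined protocol and SAP*

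**What the plan says.** The Study objective concerns "adolescent risk of using four classes of tobacco products: cigarettes, ENDS, smokeless tobacco, and LCCs". Under Study design, the three conditions differ in the size of one power wall and in the number of products on it; no condition is specific to a product class.

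Under Methods, the following happened before randomization: "Participants completed a baseline questionnaire that assessed demographics, tobacco product cognitions, smoking and tobacco use, and convenience store shopping habits". On who could take part, the text says only "Interested individuals completed a telephone screening to determine eligibility". It states no rule on tobacco use, and it does not give the share of participants who had used any product.

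The Statistical analysis plan describes the outcome models: "we used logistic regression to evaluate the relationship between the experimental conditions and post-RSL shopping risk of using cigarettes; ENDS LCCs, and smokeless tobacco". On prior use it says "Lifetime use of each product under investigation was included in the appropriate model as a covariate", coded "0 = no use; 1 = any lifetime use". Age and education are added because they are linked to tobacco use: "these variables were also included as covariates". No term for use of the other three products is listed.

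**The concern.** In the cigarette model, a participant who has used ENDS but never cigarettes has code 0, and so does one who has never used tobacco in any form. The same holds for the ENDS, LCC and smokeless models. If use of one product predicts risk for another, the level coded 0 mixes people with quite different baseline risk, and the model has no term to separate them.

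The plan's own reason for choosing age and education is their link to tobacco use. Use of another tobacco product plausibly meets that test at least as directly. The variable also appears to be in hand: tobacco use is asked about at baseline, and each of the four models already needs lifetime use of its own product.

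At stake is power for the planned contrasts of each reduced display with the status quo. The odds ratio is non-collapsible, so omitting a prognostic covariate from a logistic model pulls the conditional odds ratio towards 1 even when the arms are perfectly balanced.

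**Working it through.** **No figure to reproduce.** The documents give no sample size, power, alpha, outcome rate, effect size or use rates. Both checks below rest on assumptions and show only the range.

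**Check 1: one contrast, with and without other-product use.** Assumptions: two equal arms; control risk 25% in participants who never used any tobacco; true conditional odds ratio 0.6; other-product use in 20-40%; outcome odds ratio for other-product use 1 to 6; two-sided 0.05; sample size set so that the adjusted contrast has 80% power. For simplicity, index-product use, age and education are left out.

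The cell with 40% other-product use and odds ratio 6, by hand:

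1. Control odds are 0.25/0.75 = 0.333 in never-users and 0.333 × 6 = 2 in other-product users. Risks: 0.250 and 0.667.
2. Reduced-display odds are 0.333 × 0.6 = 0.2 and 2 × 0.6 = 1.2. Risks: 0.167 and 0.545.
3. Average risks: control 0.6 × 0.250 + 0.4 × 0.667 = 0.417; reduced 0.6 × 0.167 + 0.4 × 0.545 = 0.318.
4. Odds ratio without the covariate: (0.318/0.682)/(0.417/0.583) = 0.653, against 0.6 with it.
5. Variance of the log odds ratio, per participant. Without the covariate: 1/(0.5 × 0.417 × 0.583) + 1/(0.5 × 0.318 × 0.682) = 17.45, square root 4.18. With it, the information is the sum over the two use groups of v0·v1/(v0 + v1), where v = cell share × p(1 − p): 0.0239 + 0.0234 = 0.0474. The variance is 21.1, square root 4.59.
6. Standard-error ratio: 4.18/4.59 = 0.91. The standard error is smaller without the covariate.
7. Ratio of test statistics: (ln 0.653/ln 0.6)/0.91 = (0.426/0.511)/0.91 = 0.917. Relative efficiency: 0.917² = 0.84.
8. Power: Φ(0.917 × 2.80 − 1.96) = Φ(0.61) = 73%, where 2.80 = 1.96 + 0.84.

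The same steps for the other cells:

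| Other-product use | OR of other use | OR without covariate | SE ratio | Relative efficiency | Power |
|---|---|---|---|---|---|
| 20% | 2 | 0.605 | 0.99 | 0.98 | 79% |
| 20% | 4 | 0.623 | 0.96 | 0.93 | 77% |
| 20% | 6 | 0.640 | 0.93 | 0.88 | 75% |
| 40% | 2 | 0.607 | 0.99 | 0.98 | 79% |
| 40% | 4 | 0.631 | 0.95 | 0.90 | 76% |
| 40% | 6 | 0.653 | 0.91 | 0.84 | 73% |

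At an odds ratio of 1 for other-product use, nothing changes: 0.600 and 80%.

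**Check 2: index-product use already in the model.** Assumptions: 150 per arm; two-sided 0.05; true odds ratio 0.50; control risk 30% or 50%; index-product use 20% with outcome odds ratio 4; other-product use 80% among index-product users and 10-50% among the rest; odds ratio for other-product use 1 to 8. Without the covariate the estimated odds ratio is 0.50-0.57. Effective sample size is 98-99% at an odds ratio of 2, 91-96% at 4 and 82-91% at 8. The power lost is 0 to about 9 points. Index-product use therefore does not stand in for other-product use.

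**Null case.** With no display effect, both models in check 2 return an odds ratio of 1.00.

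**The case against.** The strongest reply is that nothing here is invalid. Four stronger readings are tempting, and the documents support none of them.

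- *Other-product users are miscoded or treated as tobacco-naive.* Code 0 means no lifetime use of the index product, and that is true of someone who has used only ENDS in the cigarette model. The plan never calls that level tobacco-naive and claims no estimate within it.
- *All users of another product fall into code 0.* An ENDS user who has also tried cigarettes is coded 1 in the cigarette model. The point concerns only those who never used the index product.
- *The comparison is confounded or the test is too liberal.* Conditions were randomized, and the null is preserved. The odds ratio without the covariate answers a more marginal question, and answers it validly.
- *Precision is lost.* The standard error is slightly smaller without the covariate (ratio 0.99 to 0.91 in check 1). The loss is in the size of the conditional effect and in power.

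It can also be said that the size is unknown. Eligibility by tobacco use is not stated, although a covariate with a level for any lifetime use implies that some users were expected. The 73% arises only in the most extreme cell of check 1. A reviewer can always name one more covariate, and because the SAP is written in the past tense, a change to the main models now may be post hoc.

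All of this stands, and it limits the point. It does not remove it: the variable is recorded at baseline, is plausibly prognostic and meets the plan's own reason for adjustment.

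**Conclusion.** The point holds as a modest loss of efficiency. Each model adjusts for index-product use, age and education only, so it cannot separate users of other products from never-users of all tobacco among those coded 0. The conditional odds ratio is pulled towards 1 and some power goes with it.

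Under check 1 the loss from 80% power is about 1 point if other-product use has an odds ratio of 2, 3-4 points at 4 and 5-7 points at 6, and none if it does not predict the outcome. These figures depend wholly on assumed rates and effects. The true loss could be negligible if other-product use is rare or weakly predictive, or if age and education already carry much of its information. The randomized comparison remains valid.

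**What to change.** In each of the four models, keep lifetime use of the index product and add one covariate: lifetime use of any of the other three products (0 = none; 1 = any). If the models have already been fitted, as the tense of the SAP suggests, report this as a labelled sensitivity analysis beside the planned result. State eligibility by tobacco use and tabulate any-product lifetime use by condition, so that a reader can judge how much the covariate could matter.

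The cost is a sentence in the SAP and one degree of freedom per model; no new data should be needed. The downside is possible instability in a model with few events, because the added term is likely to be correlated with index-product use. The documents give no event counts, so check them for each product before the covariate is used.

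### Does the plan need a risk-scale effect measure and a small-versus-medium comparison to answer its objective?

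*Combined protocol and SAP*

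**What the plan says.** The Study objective paragraph says the trial will "investigate the extent to which reducing the size of the tobacco powerwall display reduces" adolescents' risk of future tobacco use.

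The Study design paragraph introduces the arms with "The experimental conditions that we will compare in this study are", and names a large display as the status quo or control. The two reduced arms are "small power wall with a small number of products displayed, and a medium sized power wall with a medium number of products displayed". Display size and number of products therefore change together. Under Methods, "Participants were then randomized to one of the three experimental conditions".

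In the Statistical analysis plan, "we used logistic regression to evaluate the relationship between the experimental conditions and post-RSL shopping risk of using cigarettes", and likewise for ENDS, LCCs and smokeless tobacco. Lifetime use of the product, age and education are covariates. The only between-condition comparison described is the closing sentence: "Each reduced tobacco powerwall condition was compared to the all status quo/control condition (reference) using planned contrasts".

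No effect measure (odds ratio, risk difference, risk ratio or standardized risk) and no confidence interval is named. No comparison of the two reduced arms and no ordered test is described.

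**The concern.** Two things stand out on a first reading.

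- **Scale.** The objective asks about extent and is phrased in terms of risk. The natural output of these models is a conditional odds ratio, and the same odds ratio corresponds to very different risk reductions depending on the control risk. A reader who wants to know how many fewer young people are at risk would have to guess.
- **Unused ordering.** Three graded displays invite the question of whether the larger reduction does more than the moderate one. If the small display were significant against control and the medium one were not, a reader might conclude that small beats medium. Two separate tests against control do not support that conclusion.

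At stake is how the result is read: its size in absolute terms, and any ranking of the two reduced displays.

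**Working it through.** The plan states no sample size, alpha, control risk or effect size, so there is no figure of its own to reproduce. Every numerical input below is assumed and serves only to show the size of the issue.

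**1. From odds ratio to risk.** With control risk p0, the reduced-arm odds are OR × p0/(1 − p0), and p1 = odds/(1 + odds). For OR = 0.60:

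| Control risk p0 | Reduced-arm odds | p1 | Absolute reduction | Relative reduction |
|---|---|---|---|---|
| 10% | 0.067 | 6.25% | 3.8 points | 38% |
| 20% | 0.150 | 13.0% | 7.0 points | 35% |
| 40% | 0.400 | 28.6% | 11.4 points | 29% |
| 60% | 0.900 | 47.4% | 12.6 points | 21% |

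An odds ratio without the arm risks leaves the absolute size open. The arm percentages close most of that gap, and nothing in the plan prevents their being reported.

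**2. Small versus medium from two control contrasts.** The point estimate is already implied: OR(small vs medium) = OR(small vs control) / OR(medium vs control). Its standard error needs the covariance of the two estimates, which the fitted model holds. If the three arm-level variances are equal, all pairwise standard errors are equal and z(small vs medium) = z(small) − z(medium).

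- Small p=0.04 gives z=2.054; medium p=0.20 gives z=1.282. The difference is 0.77, p=0.44.
- With small fixed at p=0.04 and both effects in the same direction, medium p-values of 0.05, 0.50 and 0.90 give direct p-values of 0.93, 0.17 and 0.054. The direct p reaches 0.05 only when medium's p is about 0.925.
- With a log-odds-ratio standard error of 0.30, the log OR is −0.772 × 0.30 = −0.232. The OR is 0.79, 95% CI 0.44 to 1.43.

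This is a general fact about comparing p-values. It would harm this trial only if the plan intended to rank the reduced arms that way.

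**3. Does the plan ask for that ranking?** The objective sentence refers to "the extent to which reducing the size of the tobacco powerwall display reduces adolescents' risk of future use of tobacco", which sets a reduced display against an unreduced one. The three arms appear only in the design paragraph, where the large display is labelled as control. Saying that three conditions will be compared does not promise every pairwise comparison. The planned contrasts put each reduced arm against control, which matches the objective.

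**4. What a third contrast would yield.** Take 100 per arm, control risk 40%, OR 0.50 for small and 0.70 for medium, so arm risks are 40%, 25% and 31.8%. With SE = √Σ 1/(n p(1 − p)) and power ≈ Φ(|log OR|/SE − 1.96):

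- Small vs control: 0.693/0.308 = 2.25, power 61%.
- Small vs medium: 0.336/0.315 = 1.07, power 19%.

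The count of contrasts would rise from 2 × 4 = 8 to 3 × 4 = 12, for a comparison with little power under these assumptions.

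**5. Would a trend test do better?** A (−1, 0, 1) contrast on the three-category model is the small-versus-large contrast, which is already planned. A one-slope logistic trend is a different test unless the variances are equal. With 150 per arm and assumed risks of 20%, 10% and 10% for large, medium and small, it gives |z|=2.52 against 2.38 for small vs large. Neither shows whether small does more than medium.

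**The case for a change.** The strongest case for a change is that the objective speaks of the extent of a risk reduction, and a plan that names no effect measure or interval leaves that answer to be chosen later. Naming the measure would cost a line of text, and standardized risks, risk differences and the extra contrast need only a few lines of code on models already fitted. If the four products differ in baseline risk, equal odds ratios would also mean unequal amounts of risk reduced.

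The factual part stands: none of these items is named anywhere in the document. Arm-level risks with intervals would help readers, and so might a small-versus-medium estimate labelled exploratory. Three points keep this from becoming a required change.

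- The odds ratio is a legitimate measure of extent. No test here is biased or invalid because of the scale.
- The plan does not say how the risk-of-use outcome is scored or made binary. A count of young people at risk has no clear meaning on any scale until that is settled, so adding a risk difference would not by itself deliver the clarity sought.
- The analysis section is written in the past tense. If the analysis is done, any added contrast would be post hoc, and it would describe the combined change in display size and product number, not size alone.

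**Conclusion.** No change to the plan is needed. The omission is real, but it is one of reporting detail that analysts can fill sensibly. Followed exactly as written, the plan compares each reduced display with the status quo by a valid method and answers its objective on the odds scale. The ranking of small against medium is a question the plan does not pose.

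The possible misreading is not trivial in size: 3.8 to 12.6 points for one odds ratio over control risks of 10% to 60%, and p=0.44 behind an apparent contrast of 0.04 with 0.20. Those figures rest wholly on assumed risks and p-values and, for the second, on equal standard errors with a shared control. They are a reason for care in reporting and do not show an error in the analysis. The conclusion would differ if the plan had undertaken to rank the reduced displays, or had ruled out reporting arm-level risks; it does neither.
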